### **Real-time data capture**

All 20 US patients will be invited to take part in an app-based real world data capture activity. It is anticipated that of the 20 interview participants, a sub-set of ten will meet the inclusion criteria for this task. Five of the ten participants (50%) will take part in the app task prior to their interview and the remaining five participants (50%) will take part in the app task following their interview. Eligible participants will receive instruction and supporting documentation on how to download and access the application via their smartphone or tablet. Participants will be required to take part in the real-time data capture exercise over the course of 10 days and during this time a series of approximately 10 questions/tasks will be fielded to participants via the application to explore the experience of the symptoms, HRQoL impacts and treatment of nasal polyps and any day-to-day variability that exists these experiences in 'real time'. Some questions/tasks may be issued daily over the 10 days and others may be issued once. Examples of the types of questions that might be asked to participants via the application are documented in Appendix 9. Each task will take no longer than 5-10 minutes to complete and participants will be able to provide responses to the questions/tasks fielded to them using a variety of methodologies including video, audio, text and photographic responses.

Once recorded, the participants can submit their responses via Wi-Fi or 3/4G and they will become immediately viewable on a response dashboard for the study researchers to track and analyses. The AV research team would be able to interact with participants via the dashboard (e.g. add new tasks, send reminders to complete a task), monitor compliance and review and run reports on received responses to questions/tasks. All data from the dashboard would be downloaded and stored by Adelphi Values. As part of this process any video or photographic data whereby the participant's face was visible would be blurred/redacted.

Germany participants will not be invited to take part in the real-time data capture app task.

For those participants who elect to take part in the app task and complete this activity prior to their interview, participants will also be asked a series of general questions at the end of their interview about their experience of the app and completing the tasks/questions over the 10-day period. For those participants who take part in the app task after their interview the same questions included in the interview about the app task will be asked during a separate brief telephone call (approximately 5-10 minutes) conducted upon completion of the app task.

Adelphi Values' qualitative interviewers who are experienced in conducting interviews with adult participants will conduct the interviews. Each interviewer will participate in a comprehensive briefing meeting to ensure that they are fully familiar with the interview guide and can anticipate difficulties that may arise during the interview. The AV project team will also be responsible for the content and management of the real-time data capture application.

### **3.3.1 Endpoints**

As this study is a low-interventional, qualitative interview study, there are no formal endpoints. Data from the interviews will be used to supplement a provisional conceptual model that has been developed from a review of qualitative literature of nasal polyps, exploring the symptoms and quality of life impacts of nasal polyps. Patients will be asked to complete the SNOT-22 questionnaire and overall and single item VAS assessment during the interview; however this is purely for cognitive debriefing purposes to explore the relevance and patients understand of the content of the assessments.

#### **3.3.1.1 Primary Endpoint**

Not applicable

#### **3.3.1.2 Secondary Endpoint(s)**

Not applicable

### **3.4 Sample Size / Power Calculations**

Where the goal of qualitative research is to provide comprehensive understanding of complex phenomena (e.g. the holistic experience disease from the patient/caregiver perspective), it is recommended that sample sizes are determined based on the concept of 'conceptual saturation' where no new concepts are identified with repeated data collection. Past research and experience suggests that conceptual saturation can typically be achieved in as few as 12 individual interviews in a relatively homogenous population.

Taking the above into account, a total of 20 participants from the US and a total of 10 from Germany will be interviewed (total sample= 30).

### **3.5 Hypotheses**

As this qualitative research study is exploratory in nature no formal hypotheses are required.

## **4 DATA ANALYSIS CONSIDERATIONS**

### **Descriptive socio-demographic and clinical characteristics**

Socio-demographic and clinical characteristics for participant collected from the demographics form and CRF respectively will be summarized. Ratio data (e.g., age) will be summarized using totals (n values), means, min/max (range) statistics and where relevant standard deviations and medians. Similarly, categorical data (e.g., gender, ethnicity, race, education levels) will be summarized using totals (n values) and percentages to represent the sample in each sub-category. Descriptive data will be summarized in tabular format.

### **Analysis of interviews**

All interviews will be audio-record and transcribed/translated verbatim. All identifiable information (e.g. participants', interviewer's and doctors' names) will be removed from the transcripts to make them anonymous and all participants will be assigned a unique participants identification code (ID).

Qualitative analysis of verbatim transcripts for the semi-structured interviews will be conducted using thematic analysis methods (CE interview data) and framework analysis (CD interview data). All interview data will be audio-recorded, transcribed and entered into ATLAS.Ti, a software package which is designed to facilitate the storage, coding, and analysis of qualitative data. This program allows the researcher to code data at different levels of analysis and search for coded data using Boolean operators. ATLAS.Ti software allows traditional qualitative analysis of transcripts, but facilitates an easier break-down and management of qualitative data into groups and assign 'codes'. Each transcript would be assessed and participant comments that pertain to the main research questions would be highlighted. Axial coding enables the relationship between concepts to be explored.

The AV project leader will review the analysis of the first two interviews with the project researcher and create a coding scheme to be used throughout the analysis process (each highlighted statement will eventually be coded). After analyzing each transcription, the coded statements are then moved into their relevant domains. A list of participant statements would be generated for each domain, all of which will contain a prefix comprising the participant's designated ID number and the corresponding transcript page from which the statement was derived. Of note, whilst the frequency of participants mentioning a particular issue may be reported, quantitative analysis of this data would not occur, since that is not the purpose of qualitative research and the sample sizes are too small to utilize the data meaningfully in a quantitative or statistical fashion.

In assessing the adequacy of the qualitative research to explore the patients' experience of nasal polyps, Adelphi Values will assess whether conceptual saturation has been obtained for the CE component of the qualitative interviews (i.e. that a point has been reached at which no substantially new themes or descriptions of the concept and no new terms are being introduced by patients). Assessment of conceptual saturation is important to ensure that all concepts of importance to participant have been elicited in the interviews and is a key means of justifying the adequacy of sample sizes used in qualitative research studies. If saturation has not been reached, additional concepts important to patients may not have been captured. The process for determining saturation involves comparison of sets of transcripts to identify any consistency or inconsistencies in the pattern elicited concepts and themes. This typically involves comparison of the findings from sets of consecutive interviews. Specifically, for this sample of 30 participants (20 in the US and 10 in Germany), five sets of six interviews will be compared. If new concepts and themes are emerging in the final set of interviews then this suggests that conceptual saturation has not been achieved and further interviews may be necessary and would be discussed with GSK.

### **Descriptive statistics for the SNOT-22 and visual analogue scales**

The SNOT-22 and VAS assessments completed as part of the CD interviews will be scored by Adelphi Values using the instrument scoring instructions. For the collected VAS assessments the research team will measure the vertical line bisection and record the corresponding score which will be factored into the instrument scoring. Instrument total scores and items scores and data from the VAS (ratio data) will be summarized using totals (n values), means and min/max statistics. At the item level the distribution of participant responses (categorical data) will be summarized using totals (n values) and percentages to represent the proportion of the sample selecting each response option. Any missing data at the item level will be summarized using total (n values) and percentages. Where relevant, data will be presented in tabular or graphical format, whichever is deemed most appropriate based on the content at the time of reporting of findings.

### **Real-time data capture analysis**

Responses to the real-time data capture data will be collected using a variety of methodologies (e.g., video, audio, text and photographic responses with captions). For audio responses these will be transcribed.

Participants responses to questions/tasks in the real-time data capture activity will be analyzed in the same way using Atlas.Ti for the qualitative interviews as outlined above. Video, free text photographic and transcribed audio responses will be entered into Atlas.Ti and assigned codes in the same manner as the verbatim transcripts to tag/code

what their content conveys. For any questions/tasks fielded to participants as part of the app with multiple choice or numerical responses options, descriptive analysis of these items will be performed and reported (e.g. mean item score, ranges etc.). For those participants who complete the app task after their interview, they will answer a series of questions via telephone about their experience of this activity. This data would also be audio-recorded, transcribed verbatim and analyzed in the same way as the interview and app task data.

The interview and app task results will be used to inform the further development of a conceptual model for nasal polyps, previously constructed based on literature review activity only. The qualitative analysis will also be used help summarize the content validity of the reviewed PRO instruments and their suitability for use with patients with nasal polyps.

### **Reporting**

Adelphi Values will prepare a single report, detailing the findings from the CE and CD interviews and real-time data capture. Within the report, anonymized patient quotes will be reported. Findings from the study may also be published in peer-reviewed journals. Again, however, only anonymized information will be reported.

## **5 LIMITATIONS**

As the study has been designed using best practice methodology advocated by the Food and Drug Administration for exploratory qualitative studies used to support clinical measurement strategies, the foreseen risk/limitations of the study are minimal but include the following:

- **Selection of participants:** potential bias is always possible when selecting interviewees; however, as outlined in sections 3.2.1 and 3.2.2 eligibility criteria and recruitment quotas will be employed to ensure the participant sample is as diverse and representative as possible given the overall study size (n=30).
- **Generalizability of data:** The participant sample (n=30) is relatively small as the planned research is primarily exploratory in nature. The sample size is typical of qualitative studies conducted in this context. Nevertheless, the findings obtained from the participant interviews cannot be extrapolated or generalized to the wider population with nasal polyps; however, they will be relevant to GSK target nasal polyp population for their planned Phase III clinical trial.
- **Real-time data capture:** The eligibility criteria for the real-time data capture task and information included within the consent form (Appendix 5) will aim to ensure that those participants who take part in this activity are willing to take part over a period of ten days and that they would feel comfortable in providing responses using a variety of methods including video, audio, photographic and/or free text

responses. As this methodology is exploratory and ethnographic in nature the quality of completion and the comprehensiveness of participant responses cannot be guaranteed. This said however, the participants will be contactable both via the app and also via email and/or telephone during the completion of the app task and as such the project researchers will endeavor to encourage the completion of all task in as thorough manner as possible (e.g. provide reminders to participants to complete their task or probes/examples if they are unsure of how to respond to a task/question).

- **Conceptual saturation:** As outlined in section 4 the CE component of the interviews will be analyzed according to the principles of conceptual saturation to assess that all concepts of importance have been elicited. Whilst conceptual saturation can typically be achieved in a sample of 12 in a relatively homogenous population, a potential limitation of the study is that conceptual saturation is not achieved across the 30 interviews. Should conceptual saturation not be achieved, discussions will be held with GSK to determine whether additional interviews should be conducted in order to achieve saturation.

## **6 STUDY CONDUCT, MANAGEMENT & ETHICS**

### **6.1 Ethics Committee/IRB Approval**

This study will be submitted to an independent ethical review board in the US for review and approval prior to any study related activities and fieldwork being conducted. The German component of this study will be submitted for ethical approval to the Freiburger Ethik-Kommission International (FEKI) board in Germany.

### **6.2 Informed Consent**

Each participant will be given full oral and written information about the nature, purpose, possible risk and benefit of the study. The participant will be given the opportunity to ask questions and allowed time to consider the information provided. Participants will also be notified of their right to discontinue their participation in the study at any time. The participant's signed and dated informed consent will be obtained using the information and consent form (ICF) (Appendix 5) before any medical information is accessed (i.e. before completion of the CRF, Appendix 4), before the participant is contacted by the recruitment agencies, and before they are asked to perform any study related activities. The participant will be provided with the ICF (Appendix 5), be allowed to read it, and given the opportunity to ask the study investigator or recruitment agencies any questions. Copies of the ICF will be signed by the recruitment agencies and the participant, with the participant given one copy to take away for their records.

### **6.3 Data Protection**

The ICF (Appendix 5) explains that the transcribed data will be stored in a computer database in a folder that is password protected for 15 years by Adelphi Values. Confidentiality of this data will be maintained in accordance with HIPAA legislation. The database will be de-identified; participants will be assigned a participant ID number in place of their name and any identifiable data will be made anonymous – such as place names, family members, etc. If participants participate in the app task, for some questions/tasks they will have the option to submit video, picture, audio and text responses. In these situations all visible faces will be blurred/redacted following analysis and prior to storage, to ensure anonymity.

The ICF also explains that for data verification purposes, authorized representatives of GSK, AV, a regulatory authority or an IRB may require direct access to parts of the hospital or practice records relevant to the study including participants' medical history. The ICF further explains that in the event that a medical emergency should occur at the time of interview, the interviewer is permitted to break confidentiality and pass information onto persons such as medical personnel, in order for the participant to receive medical treatment.

With regard to the real-time data app task, the ICF also explains that if participants choose to participate in the app task, for some questions/tasks they will have the option to submit video, photograph, audio and text responses. If they choose to take part in the app task and choose to submit videos of themselves or pictures, full anonymity of the data cannot be guaranteed if their face is visible in the recordings and images that are uploaded to Adelphi Values. If they consent to participate in the real-time data app task they agree that full anonymity of the data cannot be guaranteed. However, any data submitted via the real-time data capture task will not be shared with any individuals outside of the project team. For each app question/task they will have the option of how they respond (e.g. video, audio, photograph/text). Full anonymity and confidentiality can be guaranteed for any data files, written documents or reports that are produced about the data collected.

### **6.4 Personally Identifiable Information (PII)**

Participant data will be handled in accordance to the data protection information provided in section 6.3. All participant data (study forms, transcripts and responses to the real-time data task) will be de-identified and participants will be assigned a participant ID number. This ID number will be used to label the electronic data files and documents relevant to each participant and will be used to reference participant data in the reporting of the study findings (e.g. study reports, presentations, publications).

## 6.5 Adverse Event (AE), Pregnancy Exposure, and Incident Reporting

As this is a low-interventional study that does not involve an investigational product the occurrence of adverse events is anticipated to be none to extremely low. Adverse event reporting will be managed in line with the study-specific pharmacovigilance plan (sPVP) that will be completed and filed internally at GSK. If a participant mentions during the interview any adverse event (AE) or product complaint, whether it is considered serious or not, experienced whilst taking a product produced by GSK, this must be reported to the pharmacovigilance department at GSK. The interviewer will complete an adverse event monitoring report form (**Error! Reference source not found.**) at the end of the interview that will capture information regarding the reportable event and the GSK product involved and the role of the person reporting the event. As part of this process the interviewer will seek the participant's permission to include their contract details and the contact details of their physician on the form; however, should a participant not choose to include their contact details on the AE form, they will be informed that the AE still has to be reported, but will be done so anonymously. Any completed forms will be sent to the designated contact at GSK within 24 hours of awareness of the adverse event or adverse drug reaction.

## 7.2 External Expert/Health Care Professionals (Consultants & Research PIs)

Not applicable

## 9 APPENDICES

### Appendix 1: Patient-reported nasal obstruction VAS

The following question should be completed by the participant. Recruited participants are required to have an **overall symptom score of >50**.

[figure not shown]
**Please rate your nasal obstruction at its worst over the previous 24 hours.**

## Appendix 2: Patient-reported overall symptom VAS

The following question should be completed by the participant. Recruited participants are required to have an **overall symptom score of >70**.

**Please rate your nasal polyps symptoms at their worst over the previous 24 hours.**

[figure not shown]

### Appendix 3: Clinician-reported endoscopic nasal polyp scoring

Recruited patients should have an endoscopic bilateral nasal polyp score of **at least 5 out of a maximum score of 8 (with a minimum score of 2 in each nasal cavity)** to be eligible for participation in the study.

Clinicians will be asked to provide confirmation of each nasal cavity rating as part of the case report form.

Polyp Score	Polyp size
0	No polyps
1	Small polyps in the middle meatus not reaching below the inferior border of the middle concha
2	Polyps reaching below the lower border of the middle turbinate
3	Large polyps reaching the lower border of the inferior turbinate or polyps medial to the middle concha
4	Large polyps causing almost complete congestion/obstruction of the inferior meatus

**Appendix 4: Case Report Form**

**PARTICIPANT CASE REPORT FORM (CRF)**

**TO BE COMPLETED BY THE RECRUITING PHYSICIAN**

**(Please complete a separate form for each patient recruited to the study)**

Physician Details	
Name (printed):	_____
Date of form completion:	
 
/___/___ Month
 
/___/___ Day
 
/___/___ Year
 

What is your job title/field of specialty?	
Please specify: _____	
Please sign here: _____	

INCLUSION CRITERIA		
	Yes	No
1. Participant has received oral or injectable systemic corticosteroids in the last 4 weeks (28 days) for the management of their nasal polyps	 1	 2
2. Participant has a clinical diagnosis of bilateral nasal polyps as diagnosed by endoscopy or CT scan.	 1	 2
3. Participant is aged 18 or over.	 1	 2
4. Participant has severe nasal polyp symptoms as defined as a patient-reported nasal obstruction Visual Analogue Score (VAS) of >5 (Please ask patient to complete Appendix 1 of this protocol).	 1	 2
5. Participant has had at least one previous surgery in the past ten years for the removal of nasal polyps . Surgery in this case is defined as any procedure involving instruments with resulting incision and removal of polyp tissue from the nasal cavity (polypectomy).	 1	 2
6. Participant is currently an eligible candidate for polypectomy defined by:		
c) An overall patient-reported VAS symptom score of >7 ( Appendix 2 of this protocol).	 1	 2
AND		
d) An endoscopic bilateral nasal polyp score of at least 5 out of a maximum score of 8 (with a minimum score of 2 in each nasal cavity) (	 1	 2

ADELPHI VALUES

INCLUSION CRITERIA		
	Yes	No
e) Appendix 3 of this protocol).		
7. Participant has symptoms consistent with chronic rhinosinusitis.	 1	 2
8. Participant is currently receiving intranasal corticosteroids for management of their nasal polyps.	 1	 2
8. Participant is willing to participate in the study and provide informed consent.	 1	 2
9. Participant is an English speaker and is able to read, write and fully understand the English language.	 1	 2
10. Participant is willing to and able to attend and participate in a 120-minute interview to discuss their experiences of nasal polyps and give feedback on several symptom/impact questionnaires.	 1	 2

⚡ If **ONE** of the above answers is **NO**, the patient **CANNOT** be included in the study

EXCLUSION CRITERIA		
	Yes	No
1. Participant has a diagnosis of cystic fibrosis.	 1	 2
2. Participant has a diagnosis of eosinophilic granulomatosis with polyangiitis (also known as Churg Strauss syndrome), Young's, Kartagener's or dyskinetic ciliary syndromes).	 1	 2
3. Participant has a diagnosis of antrochoanal polyps.	 1	 2
4. Participant has a diagnosis of nasal septal deviation occluding one nostril.	 1	 2
5. Participant has acute sinusitis or upper respiratory tract infection or has had had acute sinusitis or upper respiratory tract infection in the last two weeks.	 1	 2
6. Participant has ongoing rhinitis medicamentosa (rebound or chemical induced rhinitis).	 1	 2
7. Participant has had an asthma exacerbation requiring admission to hospital in the past four weeks.	 1	 2
8. Participant is currently or has previously taken part in a clinical trial for nasal polyps.	 1	 2
9. Participant is unwilling or unable to comply with the requirements of the study or has a physical or mental condition or learning difficulties that, in the opinion of the physician, may affect the participant's ability to participate in the study, the	 1	 2

ADELPHI VALUES

	Yes	No
responses he/she might provide or their ability to provide consent.		

↪ If **ONE** of the above answers is **YES**, the patient **CANNOT** be included in the study

↪ If all inclusion criteria are **YES** and all exclusion criteria are **NO** please include the participant in the study

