Participants will be recruited through a combination of primary care physicians/general practitioners and ear, nose and throat (ENT) specialists. Physicians will identify suitable participants for the study using the case report form (CRF) (Appendix 4). Participants identified by their physician will be provided with two copies of the information and consent form (ICF) to read and sign to indicate informed consent/assent if they wish to participate in the study (Appendix 5) – one for the participant to keep and one that the recruitment agency will send to AV. Participants will be given the opportunity to consider the information provided in the ICF and to ask the recruitment agencies/recruiting physician or AV any questions about the ICF before providing their informed consent. If the participant verbally agrees to take part and also signs the ICF, they will be informed that their name and contact information will be passed to the respective recruitment agencies in each country who will contact them to screen them into the study and collect demographic information about each participant (Appendix 6), ensuring study quotas are met for obtaining a representative sample as outlined in section 3.2.2. No information will be passed to the recruitment agencies until verbal and informed consent has been obtained from the participant. After informed consent has been obtained, the participant's physician will release the CRF data to the respective recruitment agencies in each country (Appendix 4); confirming that the participant meets the study inclusion requirements, and providing additional information about the participant's clinical condition and medical history. MedQuest Global will be responsible for ensuring that

any US participant who opts in to take part in the real-time data capture activities meets the criteria as outlined in section 0.

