### **3.2.1.2 Exclusion Criteria**

Any participant presenting with any of the following will not be included in the study.

- 1. Participant has received oral or injectable systemic corticosteroids in the last 4 weeks (28 days) for the management of their nasal polyps
- 2. Participant has a diagnosis of cystic fibrosis;

3. Participant has a diagnosis of eosinophilic granulomatosis with polyangiitis (also known as Churg Strauss syndrome), Young's, Kartagener's or dyskinetic ciliary syndromes);
4. Participant has a diagnosis of antrochoanal polyps;
5. Participant has a diagnosis of nasal septal deviation occluding one nostril;
6. Participant has had acute sinusitis or upper respiratory tract infection in the last two week;
7. Participant has ongoing rhinitis medicamentosa (rebound or chemical induced rhinitis);
8. Participant has had an asthma exacerbation requiring admission to hospital in the last four weeks;
9. Participant is currently or has previously taken part in a clinical trial for nasal polyps;
10. Participant is unwilling or unable to comply with the requirements of the study or has a physical or mental condition or learning difficulties that, in the opinion of the physician, may affect the participant's ability to participate in the study, the responses he/she might provide or their ability to provide consent.

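### The CRF prints the systemic corticosteroid exclusion as an inclusion item that must be answered YES, so followed as written it admits only patients the protocol excludes

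*Combined protocol and SAP*

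**What the plan says.** Section 3.2.1.2 opens its exclusion list with "Any participant presenting with any of the following will not be included in the study". Item 1 of that list is oral or injectable systemic corticosteroids for nasal polyps within the last 28 days. The exclusion list in the synopsis carries the same criterion.

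The CRF in Appendix 4 prints that sentence, without negation, as item 1 under the heading for inclusion criteria: "Participant has received oral or injectable systemic corticosteroids in the last 4 weeks (28 days) for the management of their nasal polyps". Beneath the inclusion block the form instructs: "If ONE of the above answers is NO, the patient CANNOT be included in the study". After the exclusion block it adds: "If all inclusion criteria are YES and all exclusion criteria are NO please include the participant in the study". The CRF exclusion block begins with "1. Participant has a diagnosis of cystic fibrosis" and has no corticosteroid item.

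Section 3.2 makes the CRF the screening tool: "Physicians will identify suitable participants for the study using the case report form (CRF) (Appendix 4"). The same section relies on the released CRF data as confirmation that the patient meets the study's requirements.

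**The concern.** One sentence has opposite effects in two parts of the same protocol, and the part that reverses it is the form completed by the recruiting physician. Three outcomes are possible, all unwanted:

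- **The form is followed alone.** The sample is drawn entirely from patients whom exclusion 1 bars. Section 3.2.1 describes the criteria as broadly matching the sponsor's trial population, and section 5 says the findings will be relevant to the planned Phase III population. Both statements presuppose that the protocol's own criteria were applied.
- **Both texts are followed.** Nobody can be enrolled.
- **The physician overrides item 1.** Each correctly enrolled patient then has a signed CRF that records a failed inclusion criterion. A reader of the form alone cannot tell whether the answer reflects the patient's history or an attempt to work around the form.

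The instruments debriefed in the interview ask about the past two weeks (SNOT-22) and the previous 24 hours (VAS), so recent treatment could bear on what participants report. The documents do not allow a direction or size of any such effect to be given.

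**Working it through.** No sample-size or power figure bears on this point. Section 3.5 says "As this qualitative research study is exploratory in nature no formal hypotheses are required", so the check is one of logic and of item counts.

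**Rules compared.** Let S = systemic corticosteroids for nasal polyps in the last 28 days, I = all other inclusion items met, and X = any other exclusion present.

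- CRF (Appendix 4, both decision rules): admit if S and I and not X.
- Protocol (section 3.2.1.2 and synopsis): admit if not S and I and not X.

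| S | I | X | CRF admits | Protocol admits |
|---|---|---|---|---|
| no | no | no | no | no |
| no | no | yes | no | no |
| no | yes | no | **no** | **yes** |
| no | yes | yes | no | no |
| yes | no | no | no | no |
| yes | no | yes | no | no |
| yes | yes | no | **yes** | **no** |
| yes | yes | yes | no | no |

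Of the 8 patterns, the CRF admits 1 and the protocol admits 1. They are different patterns, so the overlap is 0. On this item, 0% of protocol-eligible patients pass the CRF, and 100% of patients who pass the CRF meet protocol exclusion 1.

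**Is this a misread table?** The item counts say not.

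| | Inclusion | Exclusion | Total |
|---|---|---|---|
| Sections 3.2.1.1 and 3.2.1.2 | 10 | 10 | 20 |
| CRF, Appendix 4 | 11 (number 8 used twice) | 9 | 20 |

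The CRF has one inclusion line more (10 + 1 = 11) and one exclusion line fewer (10 − 1 = 9). The corticosteroid item is the line that differs. It carries number 1 in the inclusion block, so bilateral polyps becomes item 2 and age item 3. The exclusion block numbers cleanly from 1 at cystic fibrosis. The line sits in the wrong block of the form itself.

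**Would a later step catch it?**

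- The recruiter's enrolment step in section 3.2 refers to the inclusion list in section 3.2.1.1, not to the exclusion list in 3.2.1.2.
- The recruiter's demographics form (Appendix 6) asks nothing about systemic corticosteroids.
- The interview guide (Appendix 7) tells the interviewer to check beforehand that the CRF is complete and that the patient meets the criteria, but it contains no separate corticosteroid question.
- CRF question 5 records oral and injectable corticosteroids for nasal polyps with start and end dates. No instruction ties it to the eligibility decision.

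**Check of the correction.** If a YES on this item bars entry, the CRF rule becomes: admit if I and not (X or S). This agrees with the protocol rule in 8 of 8 patterns.

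**The case against.** The contradiction itself cannot be argued away, but its consequences can be overstated.

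- The 0%, 100% and 30-participant figures hold only if the form is applied literally and alone. The protocol body is clear and consistent, the interviewer has an eligibility check, and question 5 holds relevant dates. A physician or recruiter might notice at the first patient. This stands as a limit on prediction. It does not rescue the form, because the later checks lean on the CRF and none asks about corticosteroids separately.
- Anyone admitted would still need an obstruction VAS above 5, an overall VAS above 7 and a polyp score of at least 5, so the sample would still be severely affected. Much of the concept elicitation covers surgery, past treatment and daily life over a period well beyond 28 days. Section 3.3.1 says the questionnaires are completed only for debriefing, and there are no endpoints. This stands: damage to the content of the findings is plausible but not shown.
- The Phase III criteria are not in these documents, and section 3.2.1 claims only a broad match. What can be shown is a departure from this protocol's own criteria.
- Item 1 is a factual question, so its answer can be recovered by checking it against question 5. This also stands, and the fix uses it.
- This is better described as a transcription error than as a deliberate design choice. That affects the label, not the need to correct it.

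**Conclusion.** The concern holds. Appendix 4 reverses an eligibility rule that the synopsis and section 3.2.1.2 state in the same words, and the reversal is complete: the sets of patients admitted by the form and by the protocol do not overlap. Followed as written, the form would admit only patients who meet exclusion 1, which would apply to all 30 planned participants. That size assumes literal use of the form without correction from the protocol text. It is not an estimate of how many ineligible patients would actually be enrolled, and no claim is made about the direction or size of any effect on the interview findings. Because the error is in the form that decides entry, it must be corrected before the form is used. This conclusion concerns consistency between the texts and takes no view on which criterion is clinically preferable.

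**What to change.** Reconcile Appendix 4 with the synopsis and section 3.2.1.2. To make the form carry out the rule the protocol states twice, move the corticosteroid item from the CRF inclusion block to its exclusion block and renumber both, which also removes the duplicate number 8. If the sponsor intended something else, the synopsis and section 3.2.1.2 must be changed so that all three places agree.

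For any CRF already completed, compare the answer to item 1 with the oral and injectable corticosteroid dates in question 5 and with the form's completion date before keeping the participant, and record the outcome.

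The cost is a one-line change to the form and its re-issue to sites. No extra patients, visits or procedures are needed.
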